2.3 Secondary Objectives and Endpoints

Secondary Objective	Endpoint(s)	Time Frame

Pilot Study - Ketamine Page 15 of 55

1.	To characterize the preliminary safety and tolerability of K-MaP in patients with stage 3 and 4 GI cancers.	 Adverse events (AEs), Unexpected AEs, and Serious AEs, by CTCAE (v.5.0). Vital signs (heart rate and blood pressure) Patient-reported outcome: challenging experiences (CEQ) 	 Day -28 through Day 35. Day 0 (multiple time points on day of ketamine administratio n). Day 0, 3-4 hours after ketamine administratio n.
2.	To assess the magnitude and durability of improvement from randomization in psychosocial distress.	 Clinician-rated outcomes: Global clinical impression of severity(CGI-S), Demoralization (DI), Mood symptoms (GRID-HAMD-6). Patient-reported outcomes: Demoralization (DS-II), Depression (PHQ9), Anxiety (GAD7), Quality of Life (FACIT-PaI-14). 	From Day -28 to Day 35.
3.	To assess the magnitude and durability of improvement from randomization in pain.	Patient-reported outcome: pain (BPI-SF)	From Day -28 to Day 35.
4.	To assess the magnitude of change from randomization in opioid analgesic use.	Patient-reported outcome: Opioid use (<24hr morphine milligram equivalence [MME])	From Day -28 to Day 35.
5.	To assess the magnitude of change from randomization in interoceptive awareness.	Patient-reported outcome: interoceptive awareness (MAIA-2)	From Day 0 to Day 7

Pilot Study - Ketamine Page 16 of 55

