 *The reliability of abstinence should be evaluated carefully with the participant in relation to their general lifestyle. An additional acceptable birth control method should be discussed with the participant in case they decide to engage in penile-vaginal intercourse during the course of the study.
- 11. Must agree to the following lifestyle considerations:
 - a) Continue receiving psychotherapy or other behavioral interventions for mental health as usual. Current interventions should not be stopped, and new interventions should not be started during the study period once participants are enrolled in the study.
 - b) Consume no more than a modest quantity (e.g., 1 cup) of caffeine or xanthine-containing products (e.g., coffee or tea) the morning of receiving ketamine (on Day 0/Visit 4).
 - c) Abstain from alcohol for 24 hours before receiving ketamine.
 - d) Abstain from using any nicotine-containing products (including nicotine patches) for 3 hours before receiving ketamine.
 - e) If cannabis products are used regularly, participants will be asked to continue using their regular amount but will be asked not to use cannabis within 24 hours prior to receiving ketamine.
 - f) If prescribed a regular dose of benzodiazepines, will be asked not to take their medication the morning of the ketamine administration visit.
 - g) If taking any psychostimulants (e.g., methylphenidate), will be asked not to take psychostimulant drugs (other than caffeine) the morning of the ketamine administration visit.
 - h) Will be advised to maintain their usual opioid regimen.

Pilot Study - Ketamine Page 19 of 55

Note: Input will be obtained from the participant's regular clinical providers on appropriate pain management for the participant during the study, particularly in the case of analgesics associated with adverse reactions of concern with ketamine (e.g., tramadol and any opioid may increase the risk of respiratory depression from ketamine).

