After two MaP sessions, participants will receive ketamine on Day 0. This session will last about 4 hours. Participants will arrive to the Neurosciences Clinical Research Unit (NCRU) of the Sandler Building at UCSF Mission Bay, where they will be oriented to the treatment room for this study, which will contain a couch or bed for the participant to lie on in a private setting. Participants will hand over their shoes, keys, wallet, and phone to the study clinicians for safekeeping; these will all be returned to the participant upon completion of the treatment session. They will then complete all prerandomization assessments described in Section 6 of this study protocol. The ketamine session will be audio and video recorded, but participants will have the option of requesting that the recording be paused momentarily if they wish to discuss matters that are too personal to be recorded. There will be an on-site study physician (MD or DO) with 1) experience in the management of psychiatric emergencies and 2) experience or certification in the management of cardiovascular emergencies. Ketamine, its administration, and the medication visit will be paid for by the study and will not be billed to participants or their insurance.

Pilot Study - Ketamine Page 24 of 55

During the medication session, vital signs (heart rate and blood pressure) will be recorded at 10 minutes prior to ingestion of the oral solution ("Minute -10"), and then 30, 60, 90, 120, and 180 minutes after oral ingestion. If at 180 minutes blood pressure is meaningfully elevated compared to Minute -10, blood pressure will continue to be repeatedly assessed until it has returned to near its Minute -10 measurement. Respiratory rate and oxygen saturation will be assessed as needed.

In the event of elevated blood pressure prior to study drug administration

If the Minute -10 assessment (the mean of at least two readings separated by at least 2 minutes) of blood pressure exceeds either 140 systolic or 90 diastolic, periodic blood pressure readings will be obtained (e.g. at 5-minute intervals) to determine if the elevation may be temporary (e.g. due to anticipatory anxiety). If blood pressure decreases to (or below) 140 systolic and 90 diastolic within 20 minutes, study drug administration will proceed.

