5.1.1 Rescue Medications

The study site will have rescue medications on-site for use, as needed, during the ketamine administration visit. Rescue medications will be obtained locally. The following rescue medications may be used:

- Benzodiazepine for acute, severe anxiety or agitation not relieved by verbal de-escalation.
- Lorazepam 1-2mg PO or Diazepam 5-10mg PO
- Olanzapine for acute, severe psychosis or agitation not relieved by verbal de-escalation.
- Zyprexa Zydis (olanzapine) 5-10mg SL
- Olanzapine 10mg vial (5mg/mL) IM
- Clonidine for hypertensive urgency not thought to be associated with anxiety.
- Clonidine 0.1-0.2mg PO
- Nitrogylcerin for acute angina pectoris.
- Nitroglycerin 0.4mg SL
- Ondansetron for nausea or vomiting and/or as pre-treatment 30-60 minutes prior to ketamine
 dosing for participants who report being prone to medication-induced nausea or who regularly
 experience nausea associated with pre-existing medical conditions.
- Ondansetron 4-8mg SL

Although the use of rescue medications is allowable to protect the safety and well-being of study participants and staff during the ketamine administration visit, the use of rescue medications is not expected to be necessary in this study. If used, the date and time of rescue medication administration as well as the name and dosage of the rescue medication must be recorded.

6 Study Procedures and Schedule of Events

Assessment Plan

Patient-reported outcomes of demoralization (DS-II), depression (PHQ-9), anxiety (GAD-7), Quality of Life (FACIT-Pal-14), pain (BPI-SF), and opioid use (<24hr morphine milligram equivalence (MME), will be obtained at baseline, immediately prior to randomization (on Day 0), and post-ketamine at follow-up assessments on days 7, 14, and 35. In addition, a patient-reported outcome of interoceptive awareness (MAIA-2) will be obtained once immediately prior to randomization (on Day 0) and post-ketamine at follow-up assessment on Day 7.

As an objective measure of cardiac interoceptive accuracy, an 8-minute heartbeat detection (HBD) task will be conducted with participants while measuring their peripheral physiology using electrocardiography (ECG), respiratory rate (RR) and skin conductance (SC) monitoring, twice on Day 0—once at least 15 minutes prior to dosing of the oral solution and a second time at least 3 hours following dosing of the oral solution.

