- Cogulation tests: PT/INR (for patients with a history of cirrhosis or GI bleed within past 6 months)
- Renal function: Creatinine.

Pilot Study - Ketamine Page 33 of 55

³ The following laboratory tests are required at baseline:

⁴ EKG is required at baseline.

⁵ DS-II will be measured two times before enrollment. Once over the phone after verbal waiver of consent, and tagain, ≥7 days apart, after the participant has signed the informed consent form and started screening procedures. DS-II will also be measured at Visits 4 (before Ketamine administration), 6, 8, and 9.

	≥7, ≤28 days before Enrollment	Day -28 to -7	Day -13 to -4	Day -12 to -1	Day 0	Day 3 +/- 2 days	Day 7 +/- 2 days	Day 11 +/- 2 days	Day 14 +/-2 days	Day 35 +/- 2 days
	Phone Screening	V1 [Enrollment/ Baseline]	V2 [MaP Session 1]	V3 [MaP Session 2]	V4 [Randomization/ Ketamine]	V5 [MaP Session 3]	V6	V7 [MaP Session 4]	88	۸9
PHQ9, GAD7, BPI-SF, <24hr MME,		Х			х		х		x	х
MAIA-2					х		х			
FACIT-Pai14		Х			х		х		х	х
CGI-S, DI, GRID-HAMD6		х							х	х
MEQ, CEQ					х					
MaP Therapy Session ⁶			х	х		х		х		
Ketamine therapy (day of administration) ⁷					x					
HBD Task ⁸					х					

Pilot Study - Ketamine Page 34 of 55

⁶ It will be recommended that att least one MaP session prior to Day 0/Visit 4 occur in-person (i.e., MaP sessions on Visit 2 or 3).

⁷ The ketamine administration visit will last approximately 4-5 hours. Patients will leave the premises once they are deemed to be free of the acute effects of ketamine, at least 3 hours have passed since ingestion of the oral drug-cranberry juice solution, and the study team confirms they are in the presence of a caregiver. In the event that a participant did not arrange a caregiver to accompany them home, the participant will be required to stay with the study staff and will be escorted outside by a study team member who will accompany them home in a taxi, Lyft, or Uber.

⁸ The Heartbeat Detection (HBD) task will be administered by a trained provider twice on the day of ketamine dosing. The tasks takes about 8 minutes to complete and will administered once a least 15 minutes prior to receipt of the oral drug-cranberry juice solution and again at least 3 hours after receipt of this oral solution.

	≥7, ≤28 days before Enrollment	Day -28 to -7	Day -13 to -4	Day -12 to -1	Day 0	Day 3 +/- 2 days	Day 7 +/- 2 days	Day 11 +/- 2 days	Day 14 +/-2 days	Day 35 +/- 2 days

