9.2.3 Secondary Analysis (or Analysis of Secondary Endpoints)

Secondary Objective #1: To characterize the preliminary safety and tolerability of K-MaP in patients with stage 3 or 4 Gl cancers (i.e., pancreatic, colorectal, hepatocellular, biliary, or gastro-esophageal), we will analyze:

- Rates and types of adverse events (AEs), unexpected AEs, and serious AEs will be summarized by arm. Pre-determined criteria for assessment of tolerability to K-MaP include zero treatment-related serious adverse events.
- Across each study arm, changes in individual participant and mean heart rate (HR), systolic (SBP) and diastolic blood pressure (SBP) measurements from 10 minutes prior to ingestion of the oral solution to 30, 60, 90, 120, and 180 minutes post-oral ingestion, using random effects models that account for correlated outcomes within participants. The below thresholds will be used as indications of potential concern for patient safety. These estimates have been determined on the basis of established human safety thresholds and findings from a recent meta-analysis of hemodynamic responses to sub-anesthetic ketamine doses in patients with psychiatric conditions.[109]
 - An increase in HR baseline of greater than 25 BPM in any patient
 - o An increase in SBP of greater than 40 mm Hg in any patient
 - o An increase in DBP of greater than 25 mm Hg in any patient

Pilot Study - Ketamine Page 41 of 55

 Mean CEQ scores on the day of ketamine administration will be compared between the two study arms using ANCOVA models, discussed in the next objective.

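### On Day 0 oxygen saturation has no scheduled reading and respiratory rate has none between the drink and 3 hours; adding both to the six existing vital-sign times would be an inexpensive safety improvement

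*Combined protocol and SAP*

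**What the plan says.** Section 5 (Treatment Plan) and footnote 2 of the Study Calendar (section 6.1) fix six Day 0 times for heart rate and blood pressure: Minute -10, then 30, 60, 90, 120 and 180 minutes after the drink. Both then add: "Respiratory rate and oxygen saturation will be assessed as needed". Neither gives a trigger, a frequency or an action limit.

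The only other respiratory recording on that day belongs to the heartbeat detection task, an interoception measure. Section 6 lists electrocardiography, "respiratory rate (RR) and skin conductance (SC) monitoring, twice on Day 0". The first run is at least 15 minutes before the drink. Footnote 8 of section 6.1 places the second "again at least 3 hours after receipt of this oral solution".

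The vital-sign endpoint under secondary objective 1 (section 2.3) covers heart rate and blood pressure only. Section 9.2.3 introduces its limits with "The below thresholds will be used as indications of potential concern for patient safety" and gives three: rises of more than 25 BPM in heart rate, 40 mm Hg in systolic pressure and 25 mm Hg in diastolic pressure. It also states: "Pre-determined criteria for assessment of tolerability to K-MaP include zero treatment-related serious adverse events".

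On the risk itself, the note to inclusion criterion 11 warns that "tramadol and any opioid may increase the risk of respiratory depression from ketamine". Criterion 11(h) advises participants to stay on their usual opioids.

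**The concern.** The protocol names a respiratory risk and continues the drugs that raise it, but leaves the two direct measures of breathing to judgement. Opioid users are expected, since opioid use is a secondary outcome. During the session participants lie in eyeshades with music and are asked to interact as little as possible, so a reading taken only when needed depends on someone noticing a change.

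Two things are at stake. The first is participant safety. An ad hoc saturation value would have no scheduled pre-dose value to set it against. Blood pressure does have one: the Minute -10 assessment is "the mean of at least two readings separated by at least 2 minutes", and section 5 follows pressure after 180 minutes until it is back near that level.

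The second is description. Secondary objective 1 is to characterise preliminary safety. The arms differ in systemic exposure at the same mg/kg, so checks prompted by appearance could fall unevenly between them. Any values obtained could not then be read on the same footing.

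**Working it through.** The plan gives no figure to reproduce: section 9.1.1 says that no formal power analysis was done. The check is a count of scheduled Day 0 readings, using 12 participants and the times in sections 5, 6 and 6.1.

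**Readings scheduled**

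| Measure | Per participant | All 12 |
|---|---|---|
| Heart rate, blood pressure: time points | 6 | 6 x 12 = 72 |
| Oxygen saturation at those times | 0 | 0 of 72 |
| Respiratory rate as a vital sign | 0 | 0 of 72 |
| Respiratory rate in the heartbeat task | 2 | 2 x 12 = 24 |
| Respiratory rate at minutes 30, 60, 90, 120 | 0 of 4 | 0 of 4 x 12 = 48 |

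**Where the gap lies.** The injection follows the drink by 10 minutes (section 5). Minutes 30, 60, 90 and 120 are therefore 20, 50, 80 and 110 minutes after the injection. Section 5 expects drug effects to begin wearing off at 1.5 to 2 hours, so these four times cover the acute period.

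**Exposure by arm.** Section 1.3 gives bioavailability as 93% intramuscular and 10-17% oral. The ratio is 93/17 = 5.5 to 93/10 = 9.3.

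**Dose against the label.** Section 1.3 gives the label's intramuscular range as 6.5-13 mg/kg. The trial's 0.5 mg/kg is smaller by a factor of 6.5/0.5 = 13 to 13/0.5 = 26.

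**Effect of the fix.** Two measures at six times give 12 recordings per participant, or 12 x 12 = 144. About 24 of these (respiratory rate at Minute -10 and at 180) fall near the heartbeat-task recordings. The other 144 - 24 = 120 are at times with nothing comparable: 72 saturation values and 48 respiratory rates.

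**The case against.** The emphasis on heart rate and blood pressure is reasoned. The safety background in section 1.2 is largely hemodynamic and psychological, and section 5 names hypertensive crisis as the likeliest non-psychiatric serious event. Many controls lower the respiratory risk:

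- Section 1.3 promises continuous monitoring during the session, and the dose is 13 to 26 times below the label's intramuscular range.
- As-needed anxiolytics are barred (criterion 8, section 7.3), apart from rescue use on Day 0. Scheduled benzodiazepines are withheld on the morning of dosing, and alcohol for 24 hours (criterion 11, sections 7.1 and 7.2).
- The regular providers advise on analgesics, and exclusions cover airway problems, flash pulmonary edema, pulmonary hypertension and need for oxygen.
- Two facilitators are in the room, with a physician and an ACLS-certified clinician on site. A medical emergency leads to physician evaluation. Raised blood pressure with shortness of breath leads to a recheck and a call to the physician.
- Discharge requires freedom from acute effects and at least 3 hours since ingestion.

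All of this stands, and it is why the point is minor. It does not close the gap. The continuous-monitoring statement names no parameter, the shortness-of-breath route is tied to raised blood pressure, and none of the controls schedules a respiratory reading or yields a pre-dose saturation value.

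It is also fair to say that the plan never proposes to analyse respiratory rate or saturation, so nothing it promises goes undelivered. A reader might infer that the safety analysis fails, or that respiratory harm would go unrecorded. The documents do not support either: section 9.2.3 analyses exactly the vital signs that section 2.3 defines, and it summarises adverse events by arm, which would include a respiratory event that is recognised and recorded.

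**Conclusion.** The point holds as an optional, low-cost improvement in safety measurement. Oxygen saturation has 0 scheduled Day 0 readings. Respiratory rate has 0 of 48 between the drink and 3 hours, against 48 of 48 for heart rate and blood pressure at the same times. The protocol's own opioid warning is what makes the gap worth closing.

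A reader might go further and call the trial unsafe, or say that its tolerability conclusion is compromised. Neither follows. The documents give no frequency for a fall in respiratory rate or saturation at this dose, and none is assumed here. The rule of zero treatment-related serious adverse events does not depend on these measures.

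The counts assume that all 12 planned participants are dosed. With 6 per arm, the added data would support description only.

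**What to change.** In section 5 and footnote 2 of section 6.1, record respiratory rate and oxygen saturation in every participant at the six existing times (Minute -10, 30, 60, 90, 120, 180). Keep the as-needed provision for extra readings. Add that a value beyond a limit, fixed by the investigators for each measure before the first dosing, prompts a repeat reading and notification of the study physician.

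Add both measures to the CRF and to the vital-sign endpoint in section 2.3. In section 9.2.3, list the values descriptively by arm, with no model and no test. Leave the zero treatment-related SAE rule as it is.

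The cost is a protocol amendment, which section 9.6 makes subject to PRMC and IRB approval before use, and some CRF fields. There is also slight extra disturbance of a session meant to be minimally interactive, at moments when blood pressure is already being taken. No visit or time point is added.

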5.1 Dosage and Administration

Treatment with ketamine will be administered on an outpatient basis, on Day 0/Visit 4.

This session will last about 4-5 hours. Participants will arrive to the Neurosciences Clinical Research Unit (NCRU) of the Sandler Building at UCSF Mission Bay, where they will be oriented to the treatment room for this study, which will contain a couch or bed for the participant to lie on in a private setting. Participants will hand over their shoes, keys, wallet, and phone to the study clinicians for safekeeping; these will all be returned to the participant upon completion of the treatment session. The session will be audio and video recorded for subsequent behavioral analysis and rating of clinician adherence to the trial protocol. Participants will have the option of requesting that the recording be paused momentarily if they wish to discuss matters that are too personal to be recorded. There will be an onsite study physician (MD or DO) with experience in the management of psychiatric emergencies and experience or certification in the management of cardiovascular emergencies. administration, and the medication visit will be paid for by the study and will not be billed to participants or their insurance. The participant will be randomized to ingest liquid ketamine vs. an equivalent mL quantity of normal saline (placebo) mixed with cranberry juice (prepared by unblinded study staff) and then be administered an intramuscular injection (prepared by unblinded study staff) 10 minutes later. Participants who received oral ketamine 0.5mg/kg will be administered normal saline via IM injection while those who received normal saline (placebo) in cranberry juice will receive ketamine 0.5 mg/kg IM. Following this injection, participants will be moved from the medication administration room into the treatment room via wheelchair, transferred to the couch, and instructed to close their eyes while wearing eyeshades and listening to a preselected music playlist via headphones and speakers. The participant will be instructed to focus their attention internally and to attempt to interact minimally with the two facilitators, who will be present in the room throughout the drug session but will be as nondirective as possible in their interactions with the participant. In the event of a psychologically challenging experience such as significant anxiety or confusion, the facilitators will provide verbal reassurance and, when consented to prior to the session, supportive touch (e.g., brief handholding or hand-on-shoulder). Participants will have been instructed in the preparatory therapy session to notify the study therapists if during the treatment they feel anxiety or fear.

Ketamine preparation

On Day 0, an unblinded preparer will draw up a 0.5 mg/kg dose of liquid ketamine solution into a syringe. They will also draw up an equivalent mL quantity of normal saline in an identical syringe. Using a computer-generated randomization scheme, they will then mix either the liquid ketamine or normal saline solution into a cup of cranberry juice. This drug-cranberry juice admixture and the second syringe (containing either ketamine or saline solution) will then be handed to a blinded study therapist, who will administer the medications to the study participant.

Investigational Product	Premedication; precautions	Dose	Route	Schedule
Ketamine	N/A	0.5 mg/kg	Oral or Intramuscular	One dose, on Day 0/Visit 4

Pilot Study - Ketamine Page 27 of 55

5.1.1 Rescue Medications

The study site will have rescue medications on-site for use, as needed, during the ketamine administration visit. Rescue medications will be obtained locally. The following rescue medications may be used:

- Benzodiazepine for acute, severe anxiety or agitation not relieved by verbal de-escalation.
- Lorazepam 1-2mg PO or Diazepam 5-10mg PO
- Olanzapine for acute, severe psychosis or agitation not relieved by verbal de-escalation.
- Zyprexa Zydis (olanzapine) 5-10mg SL
- Olanzapine 10mg vial (5mg/mL) IM
- Clonidine for hypertensive urgency not thought to be associated with anxiety.
- Clonidine 0.1-0.2mg PO
- Nitrogylcerin for acute angina pectoris.
- Nitroglycerin 0.4mg SL
- Ondansetron for nausea or vomiting and/or as pre-treatment 30-60 minutes prior to ketamine
 dosing for participants who report being prone to medication-induced nausea or who regularly
 experience nausea associated with pre-existing medical conditions.
- Ondansetron 4-8mg SL

Although the use of rescue medications is allowable to protect the safety and well-being of study participants and staff during the ketamine administration visit, the use of rescue medications is not expected to be necessary in this study. If used, the date and time of rescue medication administration as well as the name and dosage of the rescue medication must be recorded.

6 Study Procedures and Schedule of Events

Assessment Plan

Patient-reported outcomes of demoralization (DS-II), depression (PHQ-9), anxiety (GAD-7), Quality of Life (FACIT-Pal-14), pain (BPI-SF), and opioid use (<24hr morphine milligram equivalence (MME), will be obtained at baseline, immediately prior to randomization (on Day 0), and post-ketamine at follow-up assessments on days 7, 14, and 35. In addition, a patient-reported outcome of interoceptive awareness (MAIA-2) will be obtained once immediately prior to randomization (on Day 0) and post-ketamine at follow-up assessment on Day 7.

As an objective measure of cardiac interoceptive accuracy, an 8-minute heartbeat detection (HBD) task will be conducted with participants while measuring their peripheral physiology using electrocardiography (ECG), respiratory rate (RR) and skin conductance (SC) monitoring, twice on Day 0—once at least 15 minutes prior to dosing of the oral solution and a second time at least 3 hours following dosing of the oral solution.

Patient-reported outcomes characterizing the Ketamine experience—the Mystical Experience Questionnaire (MEQ) and the Challenging Experience Questionnaire (CEQ)—will be obtained on Day 0 after the medication effects have worn off (about 1.5-2 hours after Ketamine administration).

Pilot Study - Ketamine Page 28 of 55

Clinician-rated outcomes of global clinical impression of severity (CGI-S), demoralization (DI), and mood symptoms (GRID-HAMD-6) will be assessed at baseline, immediately prior to randomization, and post-ketamine administration on days 14 and 35.

As a safety measure, the Columbia suicidality rating scale (CSSRS) will be given at every study visit (Visits 1-9, starting on Day -28 to Day 35). Trained study staff will assess the participant for onset or exacerbation of suicidal idealization or behavior. If at any time the participant is unwilling to continue the study, they will be allowed to stop (except while under the acute effects of study drug ketamine on Day 0/Visit 2). Support services from therapists and clinicians will be available to the participant at each study visit. The participant will continue receiving their regular medical care, separate from this study.

Patient-reported measures include:

- Demoralization Scale-II (DS-II): A well-validated self-report measure of demoralization [4]. This 16-item, 3-point scale has a 2-week recall period and produces a total score than can range 0-32, with higher scores indicating a greater degree of demoralization. It has also been validated for use with Spanish-speaking patients from both Spain and Latin America [5].
- Patient Health Questionnaire-9 (PHQ-9): A validated and widely-used 9-item, 4-point scale (0 = "Not at all" to 3 = "Nearly every day") that assesses depression symptom severity with a 2-week recall period [74]. Higher scores indicate worse depression. The scale has also been validated in Spanish [75].
- General Anxiety Disorder-7 (GAD-7): A validated self-report measure for the severity of generalized anxiety disorder (GAD) symptoms. This 7-item, 4-point scale (0 = "Not at all" to "3 = Nearly every day") scale has 2-week recall period. Item scores are summed to produce a total score that can range 0-21, with higher scores indicating greater severity of symptoms of GAD [76]. The measure has been validated in Spanish [77].
- Functional Assessment of Chronic Illness Therapy Palliative Care 14 Item Version (FACIT-Pal-14): A validated 14-item, self-report measure of quality of life in palliative care patients. The measure has a 7-day recall period and consists of 14-items with a 5-point Likert scale (0 = "Not at all" to 4 = "Very much") [78]. The measure has good internal consistency with a single underlying latent variable [79], and has been validated for use with Spanish-speaking patients with advanced cancer [80].
- Brief Pain Inventory-Short Form (BPI-SF): A validated and widely-used self-report measure of pain over the last 24-hours in patients with and without cancer [81, 82]. This 15-item measure consists of a 4-item, 11-point subscale measuring pain intensity (Severity); a 7-item 10-point subscale measuring impact on functioning and well-being (Interference); 2 open-ended questions measuring location of pain and type of pain treatment used; and a single-item 11-point subscale measuring the effectiveness of treatment. The BPI-SF Spanish version has been validated for use with patients from Spain with cancer-related [83] and non-cancer-related pain [84].
- Morphine Milligram Equivalents (MME): Calculates the patient's cumulative daily dose of opioids.
- Multidimensional Assessment of Interoceptive Awareness, Version 2 (MAIA-2): A validated a
 widely used questionnaire to measure interoceptive awareness [85]. This measure consists
 of 37-items using a 6-point Likert scale (0 = "Never" to 5 = "Always"). It has demonstrated
 good internal consistency and reliability for the evaluation of clinical mind-body interventions,
 with higher scores indicating increased.
- Heartbeat Detection (HBD) Task: Participant's bodily physiology will be measured with a
 respiration belt, galvanic skin conductance (SC) sensors, and EKG sensors while they perform
 an 8-minute heart beating detection task. During the first two 2-minute blocks of this task, they
 will be instructed to press a button on a keyboard each time they hear a heartbeat on the

Pilot Study - Ketamine Page 29 of 55

speaker. During the last two 2-miute blocks of this task, they will be instructed to press a button on a keyboard each time they think they are having a heartbeat. The physiological sensors are non-invasive and cause minimal discomfort. This task has been validated as a novel index of cardiac interoceptive accuracy [86, 87].

- Mystical Experience Questionnaire (MEQ): A validated self-report, 30-item, 6-point scale of mystical-type experiences, derived from surveys of subjective responses to psilocybin [88, 89]. Participants are asked to "please rate the degree to which at any time during that [medication] session you experienced the following phenomena;" each item is rated from 0 = "none; not at all" to 5 = "extreme (more than any other time in my life and stronger than 4)". The total score is calculated by the sum of all items. A higher score indicates a more mystical-type experience [90].
- Challenging Experience Questionnaire (CEQ): A validated 26-item self-report measure of challenging experiences with psychedelics, the CEQ assesses seven factors: grief (5 items), fear (6 items), subjective experience of death (2 items), insanity (3 items), isolation (3 items), physical distress (5 items), and paranoia (2 items). Each of the 26 items is scored on a 5-point Likert scale (0 = "None; not at all" to 5 = "Extreme [more than ever before in my life]"), with participants asked to "please rate the degree to which at any time during that [medication] session you experienced the following phenomena." A higher total CEQ score indicates greater psychologically adverse reactions to psilocybin [91].

Participants may complete these measures on an electronic tablet (using a REDCap survey) or by paper and pencil, whichever is their preference. In the event the participant opts for a telehealth visit, the study team may email the participant a link to the REDCap survey. Some visits must be in-person (see Study Calendar in Section 6.1 for more details).

Clinician-rated outcomes include:

- The Clinical Global Impressions Scale (CGI): The CGI is a widely-used 3-item clinician-administered measure developed by the NIMH to assess clinical change in patients in psychopharmacology trials [92]. The scale has previously been modified to detect clinical change in specific populations [93, 94]. In this trial we use the Global Impression of Severity item ("Considering your total clinical experience with patients with demoralization, how would you rate this participant's level of demoralization at this time?"), on the scale from "1 = Normal, not at all demoralized" to "7 = Among the most extremely demoralized patients" to assess specifically for change in demoralization as a secondary endpoint.
- Demoralization Interview (DI): A clinician-administered, 14-item structured interview designed from items of the Demoralization Scale-II [95, 96]. The DI has demonstrated good reliability and validity, with a threshold of 6 symptoms supporting a diagnosis of demoralization.
- GRID Hamilton Depression Rating Scale 6 (GRID-HAMD-6): The 6-item Hamilton Depression Rating Scale (HAMD-6) is a validated, brief, clinician-rated measure of the core symptoms of major depression [97, 98]. The measure is highly sensitive to change in pharmacotherapy trials. The GRID version of the Hamilton Depression scale is a structured and highly reliable version of the classic Hamilton Depression scale [99-101]. With permission from the owner of the GRID-HAMD, the International Society for CNS Drug Development, we will use the 6-items of the HAMD-6 in the GRID-HAMD format to create a brief, responsive and reliable measure of core depression symptoms for this trial.
- Columbia Suicidality Severity Rating Scale (C-SSRS): A validated 17-item scale that assesses suicidal ideation and behavior according to the Columbia Classification Algorithm for Suicide Assessment (C-CASA) [102]. The C-SSRS is made up of ten categories, consisting of binary responses (yes/no), to indicate presence or absence of suicidal ideation or behavior (e.g., Wish to be Dead or Aborted Attempt). A numerical score for the C-SSRS is obtained from the aforementioned categories. A validated version of the C-SSRS exists in Spanish [103].

Pilot Study - Ketamine Page 30 of 55

The clinician may complete their assessment in-person or over video conference/phone if the participant opts for a telehealth visit.

On Day 35, the last visit day, participants will be interviewed on the acceptability and tolerability of K-MaP. This interview will be audio-recorded and conducted with study staff, either via phone/teleconference or in-person, depending on participant preference.

The study-specific procedures and assessments are detailed in this section and outlined in the Study Calendar – Section 6.1.

Pilot Study - Ketamine Page 31 of 55

